The failure to accurately differentiate between bipolar and unipolar symptoms represents a crisis. Current assessments often fail to identify the risk of developing manic symptoms in bipolar patients who seek treatment during a depressive episode. Further, standard pharmacotherapy for unipolar depression can trigger or exacerbate manic symptoms (Almeida & Phillips, 2012; Cusin et al., 2007). Given that manic episodes can result in devastating financial, legal, and professional consequences as well as heightened risk for self-destructive behavior, the need to understand the pathophysiological mechanisms that differentiate unipolar and bipolar depressive symptomatology is crucial (Almeida & Phillips, 2012; Cusin et al., 2007; Valenti et al., 2012).

The current proposal was developed to address these limitations by taking a transdiagnostic approach focused on the key domain of Reward Learning within the PVS matrix. As summarized in the RDoC workshop proceedings, Reward Learning cuts across several DSM

diagnoses, and is described as “*a process by which organisms acquire information about stimuli, actions, and contexts that predict positive outcomes*”. Reward and reinforcement learning has been strongly linked to a wide range of disorders, as well as individual symptoms involving anhedonia, substance use, impulsivity (e.g., Barch & Dowd, 2010; Mason et al., 2012; Robinson & Berridge, 2008).

II. SPECIFIC AIMS

a. Objectives and hypotheses

Specific Aim 1: To investigate reward learning across four units of analyses within the mood disorder spectrum. One hundred sixty (n=160) individuals seeking treatment for mood disorders at three mood disorder clinics will be enrolled, and screened with the PRT. Using normative control data from 821 control subjects, 50% (n=80) of this sample will be asked to return for subsequent study sessions. Importantly, subjects in this sub-sample will be selected so that each quintile of the normative distribution of reward learning is equally represented (n=16 per quintile). Symptom severity measures will also be acquired and used to ensure that at least 33% of the total sample exhibits some degree of manic/hypomanic symptoms or severe depression. This sub-sample will then be further tested across four units of analysis: molecules, circuits, physiology, and behavior. Data will also be collected on 32 healthy controls, who will serve as a reference point for all measures.

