Patient recruitment will be performed at the MGH DCRP and BCRP under the supervision of Drs. [name] and [name], respectively, and at the McLean Hospital Schizophrenia and Bipolar Disorder Program under the supervision of [name]. Healthy controls will be recruited by members of [name] laboratory, which is located in the Center for Depression, Anxiety and Stress Research at McLean Hospital. Prospective healthy control subjects will undergo a phone screen, which will include an overview of study details along with questions to assess inclusion/exclusion criteria. Eligible individuals will be invited to [name] lab to complete two testing sessions involving computer tasks (such as the PRT), clinical interviews, an EEG session and a neuroimaging session. Informed consent will be collected at these sessions. **Importantly, no subject will be asked to delay or stop treatment for the purpose of participating in the studies described in this proposal.**

IV. SUBJECT ENROLLMENT

a. Methods of enrollment

One hundred sixty (160) individuals between 18 and 65 years old who meet all inclusion and exclusion criteria and are currently experiencing depressive and/or manic or hypomanic symptoms will be recruited from the Depression Clinical and Research Program (DCRP; Director: [name]) and the Bipolar Clinical and Research Program (BCRP; Director: [name]) at Massachusetts General Hospital (MGH). Additional recruitment will occur from the Schizophrenia and Bipolar Disorder Program (SBDP; Clinical Director: [name]) and Center for Depression, Anxiety and Stress Research (CDASR; Director: [name]) at McLean Hospital. After providing written informed consent, these patients will first perform a computer task, the Probabilistic Reward Task (PRT), to determine their eligibility to continue in the study. Of the 160 patients screened, 80 will be brought back for further testing. In addition to this patient sample, 32 psychiatrically healthy individuals will be enrolled from the community.

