For patient participants (n=160), data from the PRT will be immediately classified relative to norm-referenced data from our normative database, using a gender-specific cutoff for each quintile to determine subject eligibility to continue in the study. From the initial sample of 160 participants who completed the screening session including the PRT, 50% (80) will be selected to continue for the behavioral and neuroimaging sessions. Importantly, subjects in this sub-sample will be selected so that each quintile of the normative distribution of reward learning is equally represented (n=16 per quintile). For comparison to the treatment-seeking individuals with mood disorders, 32 psychiatrically healthy and demographically matched individuals will be recruited and will also complete the PRT.

Participants will be observed with HIPAA-compliant teleconferencing software ‘blue jeans’ or ‘vidyo’ as they complete the PRT in order to verify compliance with task instructions while not impacting performance by directly observing from the same room. Video will not be recorded, only streamed.

Saliva Sample Collection and Analysis

During the Screening Visit, after participant eligibility is established, an additional saliva sample will be collected using Oragene DNA Collection Kit (DNA Genotek, Ottawa, Canada; <http://www.dnagenotek.com/>). The participant will be asked to spit into the collection tube to the fill line (2mL sample) and close with a stopper. The samples will be assayed for genetic information by the [name] Laboratory (Director: [name]) in the Psychiatric & Neurodevelopmental Genetics Unit at Massachusetts General Hospital, which provides core services for genetic assays.

Session 2 (Behavioral Session)

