The PRT that was administered in session one will be administered again in session two, with the addition of 128-channel ERP recording in an acoustically/electrically shielded EEG booth in the PI's lab. The 128-channel EEG will be recoded using the Geodesic EGI system in an electrically shielded room. To avoid carry-over or learning effects, two different versions of the PRT that utilize different stimuli will be used for the screening and behavioral sessions. In the second version, instead of determining the length of the mouth, participants will need to decide whether a long or short ‘nose’ had been presented on the cartoon face by pressing the appropriate button. All other task parameters remain identical. Subjects will also complete a delay discounting task during EEG recording.

Sensitivity to Temporal Variation in Reward Task:

After the PRT, we will administer the STVR, a test of sensitivity to temporal variation in reward. This is a modified version of the ‘Door Task’ (Hajcak, Moser, Holroyd & Simons, 2006). Subjects engage in a guessing game where they start with two envelopes. They are told that the contents of one envelope will be paid to them immediately at the end of the session, and the contents of the other envelope will be paid to them in one month time, via a check in the mail. They can add to each envelope by playing a guessing game in which they are repeatedly presented with a graphic of two white envelopes and have to choose one to open. Immediately after choosing the envelope it changes color to either blue or orange. Subjects are told that blue means that this is an ‘immediate’ trial, in which the outcome will be added (or subtracted) from their ‘immediate envelope’ and orange means that this is a ‘delayed’ trial, in which the outcome will be added (or subtracted) from their ‘delayed envelope’. Following this, an up or down

arrow is displayed to show whether it they received a reward or a penalty. There are a total of 240 trials (120 trials in which they win 50 cents and 120 trials in which they lose 25 cents). During the task feedback-related negativity to the up and down arrows is measured and used to indicate the degree to which subjects show phasic dopaminergic firing to immediate and delayed rewards and penalties. The total test time is approximately 30 mins. Participants are paid \$16.25 at the end of this task.

Session 3 (Neuroimaging Session)

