Aim 2: For Hypothesis 2a, symptom inventories collected during follow-up interviews will be used to investigate incremental predictive validity of each unit of analysis in predicting subsequent symptoms while controlling for baseline severity. For these models, our behavioral and neuroimaging measures will be modeled using the relative weighting derived from the analyses described in aim 1. For quantitative measures (e.g., depressive and anhedonic symptoms), linear mixed effects models will be used. These models incorporate random subject effects to account for correlation among the repeated outcome measures (months 0, 3, 6); models will be fit using SAS PROC MIXED. Hypotheses concerning frequency measures (e.g., frequency of impulsive/risky behaviors) will be tested in a similar way. Models will be fit using SAS PROC GENMOD. Statistical tests and confidence intervals will be based on the “sandwich” estimator of standard errors to ensure that correlation among repeated assessments and overdispersion is accounted for.

d. Power analysis

Sample size and power calculations

Sample size determination was calculated based on observed effect sizes derived from prior studies that in our lab. Effect sizes were calculated using $\alpha = 0.05$ (two-tailed) for (1) detecting relationships between reward learning variables across different unit of analyses and reward-related symptoms (e.g., anhedonia, mania); and (2) to predict symptom severity measures in a naturalistic follow-up study. Based on these estimates and allowing for 15% patient attrition or data loss, the sample will be: 80 treatment-seeking individuals with mood disorders recruited from three clinics as well as 32 psychiatrically healthy controls.

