For group comparisons, multiple past studies using the PRT have found that unmedicated MDD subjects exhibited reduced reward learning compared to controls (Cohen's $d: -0.70$; Pizzagalli et al 2008c; Cohen's $d: -0.61$; Vrieze et al 2013a). In contrast, euthymic individuals with bipolar disorder had significantly higher reward learning relative to controls (Cohen's $d: 0.72$) (Pizzagalli et al 2008b). For the reinforcement learning task proposed for our fMRI study (Pessiglione et al 2006), we found that, relative to healthy controls, MDD subjects had significantly lower accuracy during reward learning (Cohen's $d: -1.54$). These effect sizes translate to power >0.98 for detecting group differences with the proposed sample size. For dimensional approaches, past studies have shown a strong large effect for the relationship between reward learning and anhedonic symptoms in BPD patients ($r = -0.59$). Moreover, among healthy subjects, reward learning predicted anhedonic symptoms 30-40 days later ($r = -0.41$, $p < 0.05$). In light of these effect sizes, a total of 80 individuals with mood disorders leads to a power of >0.97 of (1) detecting relationships between units of analysis and reward-related symptoms (e.g., anhedonia, mania), and (2) predicting clinical outcome in the naturalistic follow-

up study. Finally, in an fMRI study probing reward processing, unmedicated MDD subjects showed weaker activation than controls to gains in the caudate ($d = -0.98$) and left Nac ($d = -0.73$) and left putamen ($d = -0.78$) during reward anticipation (Pizzagalli et al 2009), yielding a mean effect size of -0.87. In light of an average ES of 0.83 in the fMRI study, a total of 80 individuals with mood disorders and 32 healthy controls leads to a power >0.97 of detecting group differences.

VII. RISKS AND DISCOMFORTS

The risks associated with participation in this study are minimal, and every possible precaution is being taken to further reduce potential risks, as described below:

Behavioral component. We foresee no risks from the behavioral tasks required for the proposed research.

Genetic component.

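### Section VI.d: the power above 0.98 claimed for group differences holds for one of the four effects listed; the three PRT effects give 0.82 to 0.93 at 80 v 32

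*Combined protocol and SAP*

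**What the plan says.** Section VI.d (Power analysis) sets a two-tailed 0.05 level and fixes the sample: "Based on these estimates and allowing for 15% patient attrition or data loss, the sample will be: 80 treatment-seeking individuals with mood disorders", with 32 healthy controls. It does not say whether 80 is the number before or after the 15% allowance.

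It then cites earlier patient-control differences. On the PRT these are d = -0.70 and d = -0.61 for unmedicated major depression and d = +0.72 for euthymic bipolar disorder. For accuracy on the reinforcement learning task it cites d = -1.54 for major depression. One sentence covers all four: "These effect sizes translate to power >0.98 for detecting group differences with the proposed sample size". A later, separate statement on fMRI activation does declare an average: "In light of an average ES of 0.83 in the fMRI study".

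Other sections describe who the 80 are. Section IV.a enrols people "currently experiencing depressive and/or manic or hypomanic symptoms will be recruited", and then: "Of the 160 patients screened, 80 will be brought back for further testing". Under PRT Data Collection and Scoring in section V.a, those 80 are "selected so that each quintile of the normative distribution of reward learning is equally represented (n=16 per quintile"). Section II.a gives the controls' role: "Data will also be collected on 32 healthy controls, who will serve as a reference point for all measures".

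**The concern.** The sentence reads as applying to each effect before it, but the four differ in size by a factor of about 2.5 (1.54/0.61). Effects of 0.61 to 0.72 with only 32 controls would not be expected to give power of 0.98.

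This is the plan's only power statement for PRT differences between patients and controls. A reader would take the risk of missing such a difference to be under 2%, and could read a null PRT contrast as good evidence of no difference. The figure also says nothing about how the cited groups (one diagnosis each) differ from the sample that will be studied.

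**Working it through.** **Inputs, all from section VI.d.** Two-sided alpha 0.05; n1 = 80 patients; n2 = 32 controls; |d| = 0.70, 0.61, 0.72 (PRT) and 1.54 (reinforcement task). If 80 is the number before the 15% patient loss, n1 = 80 x 0.85 = 68.

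**Formula.** Two-sample t test. Noncentrality = |d| / sqrt(1/n1 + 1/n2), with n1 + n2 - 2 degrees of freedom. Power is the probability that the noncentral t exceeds the two-sided critical value.

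- 80 v 32: sqrt(1/80 + 1/32) = 0.2092; critical t (110 df) = 1.982.
- 68 v 32: sqrt(1/68 + 1/32) = 0.2144; critical t (98 df) = 1.984.

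**Reproducing the plan's figure.** The mean absolute effect is (0.70 + 0.61 + 0.72 + 1.54)/4 = 0.8925. Noncentrality at 80 v 32 is 0.8925/0.2092 = 4.27 and power is 0.988 (0.985 at 68 v 32). So a value above 0.98 does reproduce, but only from this mean. Other summaries at 80 v 32 do not reach it: the mean of the three PRT effects, 0.677, gives 0.894; the signed mean of all four, -0.53, gives 0.713; the mean of the four separate powers is 0.916.

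**Effect by effect.**

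| Effect | Noncentrality, 80 v 32 | Power, 80 v 32 | Power, 68 v 32 |
|---|---|---|---|
| PRT, d = -0.70 | 3.35 | 0.913 | 0.899 |
| PRT, d = -0.61 | 2.92 | 0.824 | 0.804 |
| PRT, d = +0.72 | 3.44 | 0.927 | 0.914 |
| Reinforcement task, d = -1.54 | 7.36 | >0.999 | >0.999 |

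The normal approximation at 80 v 32 gives 0.917, 0.831 and 0.931 for the PRT effects, so the choice of method does not matter.

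**Effect needed for 0.98.** |d| = 0.847 at 80 v 32 and 0.869 at 68 v 32. No PRT effect reaches either.

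**Alternative readings of the sample or test (PRT effects).**

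- One-sided test at 80 v 32: 0.895 to 0.962.
- Equal split of the 112 subjects, 56 v 56: 0.892 to 0.965.
- All 160 screened patients v 32: 0.880 to 0.959.
- Unlimited patients v 32 controls, Phi(d x sqrt(32) - 1.96): 0.932 for d = 0.61, 0.977 for d = 0.70, 0.983 for d = 0.72.

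None brings all three PRT effects to 0.98. With 32 controls, two of them cannot reach it however many patients are added.

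**What the recomputed figures assume.** Each sets all 80 patients against an effect observed in one diagnosis, in groups not chosen by the quintile rule. The planned 80 mix depressive and manic or hypomanic presentations, and VI.d gives the depressive and bipolar PRT effects opposite signs, which would partly cancel in a pooled mean. Filling the normative quintiles equally also pulls the selected patients' screening PRT distribution towards the normative one. Both features shrink a pooled patient-control difference, so 0.82 to 0.93 is optimistic for that contrast in the planned sample.

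**The case against.** The strongest reply is that the sentence is a collective statement: the same section averages the fMRI effects and quotes one power, and averaging the four absolute values here gives 0.988. That may well be how the figure arose, and on that reading the sum is right. But the average is not declared, it combines two different tasks, it treats opposite directions as one, and it passes 0.98 only because 1.54 is included. It does not describe the power for any PRT effect.

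The second reply is that nothing planned rests on the figure. This stands. VI.d ties the sample size to relationships between reward-learning measures and symptoms and to prediction at follow-up. VI.c specifies regression, canonical correlation and repeated-measures models, and names no patient-control PRT test.

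Two stronger readings are tempting, and the documents support neither. A reader might infer that the study is too small for PRT differences; yet each PRT effect keeps power of at least 0.80 on the simple reading, even at 68 v 32. A reader might also infer that quintile selection leaves almost no power for any PRT contrast. How much a difference on the session 2 PRT would shrink depends on retest correlation, diagnostic mix and patient variance, none of which the documents give. In addition, all 160 patients take the screening PRT before selection, so a contrast in that group is not affected by the quintile rule.

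**Conclusion.** The claim is wrong as written for three of the four effects it covers. PRT power is 0.82 to 0.93 at 80 v 32 (0.80 to 0.91 at 68 v 32), which is 5 to 16 points below 0.98 at 80 v 32. The implied miss risk is 7 to 18% (9 to 20% at 68 v 32) where the text suggests under 2%. The claim is correct for reinforcement-task accuracy. These results rest only on the effect sizes, sample sizes and alpha in VI.d and a two-sample t test.

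That the figures are optimistic for a pooled contrast follows from the mixed enrolment and the quintile rule. The size of that optimism cannot be worked out from the documents, and no number is put on it here. The consequence is modest: it changes how VI.d and any PRT patient-control comparison should be read, and leaves the Aim 1 and 2 analyses and the sample size as they are.

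A separate minor note: section I (Previous research) and VI.d describe bipolar patients' PRT reward learning as raised relative to controls, while the title of the source cited for that effect, in section X, describes it as reduced. The documents cannot settle which is right, and a reader should not infer that the power result turns on it: power at |d| = 0.72 is the same in either direction.

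**What to change.** In VI.d:

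1. Confine the claim of power above 0.98 to reinforcement-task accuracy (d = -1.54).
2. State PRT power per effect at 80 v 32: 0.91 for d = -0.70, 0.82 for d = -0.61, 0.93 for d = +0.72. At 68 v 32 the figures are 0.90, 0.80 and 0.91. Say whether 80 is before or after the 15% allowance, so that one set can be kept.
3. Add one sentence: these powers assume 80 patients of a single diagnosis not selected on the PRT, whereas the planned 80 are diagnostically mixed and taken 16 per normative PRT quintile, so the figures are optimistic for a pooled patient-control contrast.

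Separately, check the direction of the bipolar PRT effect against the cited source and make sections I, VI.d and X agree.

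The cost is a few reworded sentences and one citation check. No patients are added and no analysis model changes.

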Hypothesis 1: We will identify the units of analysis that show the strongest relative loading onto 3 reward-relevant symptom assessments in the areas of anhedonia, impulsivity, and mania across patients and controls.

Specific Aim 2: To investigate the predictive validity of reward learning units in a naturalistic follow-up study.

Hypothesis 2a: Relative weights for each unit of analysis for each symptom assessment area derived in Aim 1 will be used to predict the presence of anhedonic, manic and impulsive symptoms as assessed via phone interview at 3- and 6-month follow-up intervals. We predict that our units of analysis will have significant incremental predictive validity in predicting these domains while controlling for baseline severity.

Hypothesis 2b: Individuals who present at baseline with depressive symptoms but show an elevated response bias and enhanced PE signaling will show less symptom improvement following SSRI treatment in a naturalistic design (i.e., there is no treatment component to the study, but it is expected that many patients recruited through clinics will be receiving SSRI treatment).

III. SUBJECT SELECTION

a. Inclusion and exclusion criteria

General Exclusion Criteria

- 1) Suicidal ideation where outpatient treatment is determined unsafe by the study clinical interviewer. These patients will be immediately referred to appropriate clinical treatment;
- 2) Pregnant women or women of childbearing potential who 1) have not completed a negative urine pregnancy test prior to the MRI scan and/or 2) are seeking to become pregnant or believe that they may be pregnant

- 3) Serious/unstable medical illness (e.g., cardiovascular, renal, endocrine, neurologic disease);
- 4) Clinical or laboratory evidence of hypothyroidism;
- 5) History of seizure disorder, history or current diagnosis of dementia, score < 26 on the MMSE at screening;
- 6) History or current diagnosis of the following DSM-IV psychiatric illness: organic mental disorder, schizophrenia, schizoaffective disorder, delusional disorder, psychotic disorder NOS, patients with mood congruent or mood incongruent psychotic features
- 7) Lifetime history of stimulant dependence (e.g., cocaine, amphetamines)**;
- 8) Current use of Methylphenidate (Ritalin) and other ADHD medications with dopaminergic effects**;
- 9) Patients who have had electroconvulsive therapy (ECT) in the past 2 years;
- 10) Failure to meet standard MRI safety requirements;

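### The power of >0.97 for predicting outcome at follow-up is figured on all 80 patients and does not extend to Hypothesis 2b, which concerns an SSRI-treated depressed subset of unstated size

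*Combined protocol and SAP*

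**What the plan says.** Section VI.d (Power analysis) of the combined protocol and SAP sets the test level: "Effect sizes were calculated using $\alpha = 0.05$ (two-tailed"). It gives two correlations for the dimensional analyses. One is cross-sectional, the "relationship between reward learning and anhedonic symptoms in BPD patients ($r = -0.59"). The other is prospective: "among healthy subjects, reward learning predicted anhedonic symptoms 30-40 days later ($r = -0.41$, $p < 0.05"). From these it concludes that "a total of 80 individuals with mood disorders leads to a power of >0.97 of" two things, the second being "predicting clinical outcome in the naturalistic follow"-up study. No subgroup is named. The same section says that, "allowing for 15% patient attrition or data loss, the sample will be: 80 treatment-seeking individuals with mood disorders" plus 32 controls.

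Aim 2 in section II.a has two hypotheses. Hypothesis 2a predicts symptoms at 3 and 6 months while controlling for baseline severity. Hypothesis 2b says that patients who present with depressive symptoms but "show an elevated response bias and enhanced PE signaling will show less symptom improvement following SSRI treatment in a naturalistic design". SSRI use is not a condition of entry; the plan only expects that many patients will be taking one. Section III.a admits patients on stable medication and patients free of psychotropic medication. Section IV.a admits patients with depressive symptoms, manic or hypomanic symptoms, or both. Section VI.c describes an Aim 2 analysis for Hypothesis 2a and none for 2b.

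**The concern.** Predicting clinical outcome in the naturalistic follow-up is a fair description of Aim 2 as a whole, and section II.a itself places 2b in a naturalistic design. A reader will therefore take >0.97 as the power for 2b too, particularly since no other sample size, effect size or power for 2b appears anywhere. Yet the figure rests on 80 patients, and 2b can use only those who are both depressed at baseline and treated with an SSRI.

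What is at stake is how a null result would be read. Set against 97% power, a non-significant 2b result would look like good evidence that there is no such effect. In a subset of half the evaluable patients or fewer, it would be weak evidence.

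**Working it through.** **Inputs.** Two-sided alpha 0.05; |r| = 0.41 (the smaller cited correlation and the only prospective one); N = 80; 15% loss, so 80 × 0.85 = 68 evaluable. All are from section VI.d. The share of patients who are depressed and SSRI-treated is not given, so it is varied as an assumption.

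**Methods.** Fisher z: power = Φ(atanh|r| × √(n − 3) − 1.960), with atanh(0.41) = 0.4356. As a second method, the noncentral t with n − 2 degrees of freedom and noncentrality |r|/√(1 − r²) × √n = 0.4495 × √n.

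**The plan's figure.** At n = 80: 0.4356 × √77 − 1.960 = 1.863, so power is 0.969. The noncentral t gives 0.978, and simulation of bivariate normal data gives 0.970. The stated >0.97 is reproduced within rounding, using all 80 patients and one unadjusted correlation. (|r| = 0.59 gives about 1.00, so the smaller correlation is the binding one.)

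**After the plan's own loss.** At n = 68: 0.4356 × √65 − 1.960 = 1.552, so power is 0.940; the noncentral t gives 0.955.

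**Hypothesis 2b, borrowing |r| = 0.41.**

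| Assumed share of 68 | n | Fisher z | Noncentral t |
|---|---|---|---|
| 100% | 68 | 0.940 | 0.955 |
| 90% | 61 | 0.913 | 0.932 |
| 75% | 51 | 0.855 | 0.882 |
| 60% | 41 | 0.766 | 0.802 |
| 50% | 34 | 0.679 | 0.720 |
| 40% | 27 | 0.569 | 0.612 |
| 30% | 20 | 0.435 | 0.477 |

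Power of 0.80 needs 45 qualifying patients by Fisher z (41 by the noncentral t). Power of 0.97 needs 80 or 81 qualifying patients by simulation or Fisher z, which is the whole recruited sample with no loss.

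**Does the borrowed effect fit 2b?** The cited r relates reward learning to the level of anhedonic symptoms 30 to 40 days later in healthy subjects; section VI.a defines reward learning as the change in response bias from Block 1 to Block 3. Hypothesis 2b relates elevated response bias together with enhanced prediction-error signaling to symptom improvement under an SSRI in patients. Predictor, outcome and population all differ. The cited r is thus no guide to the size of the 2b effect, and the table shows only what happens if it is borrowed. With an assumed |r| = 0.30 instead, Fisher z power is 0.70 at n = 68 and 0.41 at n = 34.

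**The case against.** The strongest reply is that section VI.d never names 2b. Its opening paragraph describes the second purpose as predicting symptom severity measures at follow-up, which fits 2a better than improvement under an SSRI. On that reading nothing is misstated, and one clarifying sentence is enough. This has force, and the fix below is indeed a clarification. But the later wording, clinical outcome, is broader, nothing excludes 2b, and the use of 80 instead of 68 affects 2a as well.

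A second reply is that the qualifying share may be high, since patients come largely from mood disorder clinics. That is possible: at 90% of 68 the power is still 0.91 to 0.93. The documents do not settle the share, so no single figure can be given. Two follow-up assessments might also add some precision over a single correlation, but the plan gives no within-patient correlation from which to work this out.

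Three stronger readings are tempting and are not supported:

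- A reader might infer that >0.97 is miscalculated. It is not; it reproduces for 80 patients.
- A reader might infer that the negative sign of the cited r contradicts 2b, or that 2b has no prior support at all. The sign does not alter the power of a two-sided test. Because the two statements concern different predictors, outcomes and populations, both could be true. The most that can be said is that the cited r does not inform 2b.
- A reader might infer from the words elevated and enhanced that the plan will split patients into groups and lose power that way. No analysis of 2b is specified, and section VI.c leaves continuous or categorical coding of covariates to be decided.

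**Conclusion.** The point holds as one about the scope of a power claim, not as an arithmetic error. The figure of >0.97 belongs to one unadjusted correlation of 0.41 in all 80 patients. On the plan's own 15% loss it becomes 0.94 to 0.955, a small change. For Hypothesis 2b the stated power is not delivered unless essentially all 80 patients are depressed, SSRI-treated and retained, which the entry criteria do not ensure. Borrowing |r| = 0.41, power is about 0.86 to 0.88 at 51 patients, 0.68 to 0.72 at 34 and 0.44 to 0.48 at 20. These values rest on assumed shares of 75%, 50% and 30% of 68, and on an effect size taken from a different setting. A smaller true effect would lower them.

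**What to change.** In section VI.d, limit the second item to Hypothesis 2a and restate its power at 68 evaluable patients (about 0.94 to 0.955 for a single correlation of 0.41). Add a sentence saying that this figure does not cover 2b and that the cited correlation does not inform the size of the 2b effect. Then do one of two things for 2b: give its power over a plausible range of SSRI-treated depressed patients, with the assumed effect size stated; or make no power claim and present 2b as an estimate, a slope with its 95% confidence interval. In section VI.c, add the missing analysis for 2b, naming the analysis set and the improvement outcome, with response bias and prediction-error signaling entered as continuous scores.

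The cost is wording in VI.c and VI.d. The stated power becomes less favourable. No further patients, visits or data are needed.
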